6.1 Duration of the Study

Subjects will be on treatment for up to 24 weeks. Subjects who experience adverse reaction will discontinue study drug but will continue to complete all protocol-specified follow-up visits, assessments and evaluations. They will then continue to be followed up for the remaining duration of the study. Unless otherwise recommended by the Independent Data Review Board (IDRB) or regulatory authorities, the study will continue until it accrues a minimum of 60 subjects complete the study.

Until formal conclusion of the study, subjects, investigators and all site study personnel will be remain blinded as to treatment allocation, except in the event of a medical emergency which necessitates unblinding.

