6.3 Reasons for Subject Withdrawal

Any subject may withdraw his or her consent at any time.

Subjects will be monitored carefully during the study. Any subject who experiences an increase in ALT value greater than 3X baseline during the treatment period will be monitored weekly. If ALT values increase to greater than 5X the baseline ALT will be rechecked within 48 hours and if value remains $>$ 5X baseline, the subject will be withdrawn from the study. The subject will then be followed, and ALT, AST, prothrombin time, and total bilirubin will be monitored every 2 weeks thereafter until the value that led to the subject's discontinuation of therapy has returned to the baseline value (Baseline for prothrombin time and total bilirubin is the value obtained at the screening).

Other reasons for withdrawal from the study may include, but are not limited to the following:

- Subject is in violation of the protocol, defined as refusal or inability to adhere to prescribed dosing and/or follow-up regimen.
- Subject is lost to follow-up.
- Subject experiences a serious or intolerable AE that, in the medical opinion of the principal investigator, warrants discontinuation.
- Subject has laboratory safety assessments that reveal clinically significant worsening from baseline values.
- Subject develops, during the course of the study, symptoms or conditions listed in the exclusion criteria.
- Subject requires a medication that is prohibited by the protocol.
- Investigator or TaiwanJ Pharmaceuticals requests an early discontinuation of the trial for any reason.

The investigator may also withdraw a subject upon the request of TaiwanJ Pharmaceuticals or if TaiwanJ Pharmaceuticals terminates the study. Upon occurrence of a serious or intolerable AE, the principal investigator will confer with TaiwanJ Pharmaceuticals. If a subject is discontinued because of an AE, the event will be followed until it is resolved or until the principal investigator or sub-investigator deems the event to be chronic or the subject to be stable.

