10. SCHEDULE OF EVENTS

10.1 Tests and Evaluations

No subject may be permitted to undergo any protocol-specified investigations or interventions in this study until they have provided a signed, dated, written informed consent.

All tests and evaluations must be performed prior to that day's administration of study drug treatment. Subjects should undergo all tests and evaluations specified in the protocol, regardless of whether they remain on study drug. Insofar as possible, all blood samples should be collected at approximately the same time of day in each visit, in order to minimize diurnal variation.

The required procedures for patient evaluation at each study visit are outlined in the study. Schedule of Visits and Procedures are in Sections 10.2 and detail items in section 10.3 through 10.4.8. Detailed instructions for specific procedures are presented in Section 11.

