12.4 Toxicity Management Guidelines

The toxicity management will be based on DAIDS AE Grading system,

Hepatic toxicity:

ALL patients will have increased liver enzymes at baseline. Liver function tests will be monitored with each visit. For any elevated ALT 5-10.0 X ULN (Grade 3 or 4) on study drug, repeat testing and evaluation will be performed in 1 week. Treatment will be interrupted for drug-related Grade 3 AE until their AE Grade is less than 3. Liver function tests and assessment will be performed weekly to ensure resolution of Grade 3 AE. Study drug may be resumed following confirmation of resolution of Grade 3 AE or if investigator confirms AE is keeping with patient's underlying NASH. The investigator must assess whether or not Grade 3 AE is clinically or not clinically significant in the setting of NASH and in reference to baseline ALT levels. Increases in liver enzymes $> 3 \times$ subject's baseline will prompt retesting and patient examination within 1 week. Increases in liver enzymes $> 5 \times$ subject's baseline will prompt immediate drug discontinuation and withdrawal from study. For non-drug related Grade 3 AE, Investigator will perform further clinical management based on subject's clinical condition and/or other biochemistry results.

DAIDS Grading	Lab Value						INR	Clinical management	
	ALT *		AST		Bilirubin (total)			Non Drug Related	Drug Related
Grade 1	1.25-2.5 x ULN	and/or	1.25-2.5 x ULN	and/or	1.1-1.5 x ULN	and/or	1.2-1.3	Non treatment modification	
Grade 2	2.6-5.0 x ULN	and/or	2.6-5.0 x ULN	and/or	1.6-2.5 x ULN	and/or	1.4-1.5	Non treatment modification	
Grade 3	5.1-10.0 x ULN	and/or	5.1-10.0 x ULN	and/or	2.6-5.0 X ULN	and/or	1.5-2.0	Further clinical management will be judged by Investigator	Treatment interruption may be suggested by Investigator
Grade 4	$> 10.0 \times$ ULN	and/or	$> 10.0 \times$ ULN	and/or	$> 5.0 \times$ ULN	and/or	> 2.0	Treatment termination and withdraw	

* Subjects with elevated ALT > 10.0 ULN will be withdrawn from this study.

Discontinuation of treatment should be considered if:

- ALT or AST $> 10 \times$ ULN
- ALT or AST $> 5 \times$ ULN for more than 2 weeks
- ALT or AST $> 3 \times$ ULN and total bilirubin $> 2 \times$ ULN or INR > 1.5
- ALT or AST $> 3 \times$ ULN with the appearance of fatigue, nausea, vomiting, right upper quadrant abdominal pain, fever, rash or eosinophilia ($> 5\%$).

Other toxicities

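### Protocol Sections 6.3 and 12.4 disagree on whether study withdrawal for ALT above 5x baseline waits for a 48-hour recheck; the >10x ULN rule and the study-withdrawal wording are also inconsistent

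*Protocol*

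**What the plan says.** Protocol Section 6.3 deals with ALT only. Once a value exceeds 5x baseline, "ALT will be rechecked within 48 hours and if value remains" above 5x baseline, the subject is withdrawn from the study. ALT, AST, prothrombin time and bilirubin are then followed every 2 weeks "until the value that led to the subject's discontinuation of therapy" is back at baseline.

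Protocol Section 12.4 deals with liver enzymes generally. A rise above 5x the subject's baseline "will prompt immediate drug discontinuation and withdrawal from study". No repeat test is mentioned. The same section has rules based on ULN:

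- For ALT of 5 to 10x ULN it asks for a repeat in 1 week. It interrupts drug for a drug-related Grade 3 event and allows drug to resume afterwards.
- Above 10x ULN, the table footnote reads "Subjects with elevated ALT > 10.0 ULN will be withdrawn from this study" and the Grade 4 row reads "Treatment termination and withdraw".
- The list below the table includes the same 10x ULN threshold but opens with "Discontinuation of treatment should be considered if". Section 10.4.7 repeats the list under a heading sentence that says medication may be stopped.

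On follow-up, Section 6.1 says that a subject with an adverse reaction "will discontinue study drug but will continue to complete all protocol-specified follow-up visits, assessments and evaluations". Section 10.1 says: "Subjects should undergo all tests and evaluations specified in the protocol, regardless of whether they remain on study drug".

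**The concern.** This is the individual hepatic stopping rule in a liver trial where every subject enters with raised enzymes. Two mandatory instructions cover the same laboratory value, and a site cannot both wait for confirmation before withdrawing a subject and withdraw that subject at once. With about 12 sites, the same unconfirmed ALT could lead to a retained subject at one site and a withdrawn subject at another.

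Two related texts add to the uncertainty. The >10x ULN rule is compulsory or discretionary depending on which line of Section 12.4 is read. And both >5x baseline rules end participation in the study, whereas the protocol's general approach is to stop drug and keep observing. A subject stopped for possible liver injury is one whose later data matter, for safety and for the trial's completeness.

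**Working it through.** The plan states no figure on this point, so the check is a comparison of texts plus a small threshold illustration.

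**Step 1: the two >5x baseline rules.**

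| | Section 6.3 | Section 12.4 |
|---|---|---|
| Trigger | ALT | Liver enzymes (not defined further) |
| Recheck | Within 48 hours | None stated |
| Drug during recheck | Not stated | Stopped at once |
| Withdrawal from study | Only if confirmed | At once |

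Section 6.3 does not say that dosing continues during the 48 hours, so stopping drug on the first value breaches neither section. Withdrawal is different: Section 6.3 makes it conditional on the repeat and Section 12.4 does not. For a confirmed ALT rise both sections give the same result. For an unconfirmed ALT rise they give opposite results. For a rise in AST alone, Section 12.4 acts and the ALT rule in Section 6.3 is silent.

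**Step 2: is there an order of precedence?** Section 10.4.7 points to the toxicity section, but only as one ground on which drug may be stopped. It does not rank Section 12.4 above Section 6.3. The SAP does not address the matter.

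**Step 3: overlap with the ULN-based rules.** The documents give no ULN for ALT, so two values are assumed for illustration: 20/30 U/L (women/men), the endpoint normal range, and 40 U/L, the alternative range in SAP Section 5.2. Baselines are set just above the screening thresholds of 40 and 60 U/L.

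- ULN 40, baseline 41: 5 x 41 = 205 U/L. A value of 206 is 206/40 = 5.15x ULN. It meets three instructions together: the 48-hour recheck (6.3), immediate withdrawal (12.4), and the 1-week repeat with possible interruption and resumption (12.4, Grade 3).
- ULN 20, woman with baseline 41: 205 U/L exceeds 10 x 20 = 200. ULN 30, man with baseline 61: 5 x 61 = 305 exceeds 10 x 30 = 300. Here any value above 5x baseline also triggers the >10x ULN rule.

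Under either assumption more than one instruction applies to the same result. These are examples, not limits on who is affected.

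**Step 4: the >10x ULN rule.** The footnote and the Grade 4 row require withdrawal without a repeat. The list in Section 12.4 and Section 10.4.7 leave stopping drug to judgment. Section 12.4 also labels its 5 to 10x ULN repeat as Grade 3 or 4, although its table starts Grade 4 above 10x ULN, so whether a repeat applies above 10x ULN is not clear either.

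**Step 5: study withdrawal against continued follow-up.** Sections 6.1 and 10.1 keep subjects who are off drug in assessment. Section 6.3 itself goes on to describe the event as stopping therapy. Section 6.3.1 asks for Visit 8 and 9 assessments whenever possible; Section 10.4.6 asks for an End of Treatment visit, if possible, and one visit 4 weeks later; Section 10.4.4 asks sites to try to bring back subjects who stopped treatment for Weeks 24 and 28. These recover part of the data, but 6.3.1 and 10.4.6 do not preserve the remaining schedule or secure an MRI at Week 24.

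**The case against.** The strongest reply is that both rules are protective and largely compatible. A site can stop drug at once, recheck within 48 hours and then decide on withdrawal. Section 6.3 also lists important laboratory worsening as a separate ground for withdrawal, so early action is within its terms. Withdrawn subjects have their own follow-up provisions. Oversight is in place: Section 11.4 escalates Grade 3 or higher results for medical review, Section 12 has the Clinical Monitor go through adverse-event management with sites beforehand, and Section 13.6 provides an independent hepatologist as Medical Monitor and an unblinded review board.

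Much of this stands. It disposes of any claim that Section 6.3 keeps a subject on drug while Section 12.4 stops it. It does not settle whether withdrawal waits for the repeat: a discretionary ground in Section 6.3 permits early withdrawal but does not make it the rule, and none of the oversight provisions says which text applies.

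Three further inferences are tempting and are not supported.

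- That the conflict matters only when baseline ALT is below 2x ULN, because 5 x baseline reaches 10x ULN once baseline is 2x ULN or more. This takes the >10x ULN rule as mandatory, which the protocol does not say consistently.
- That the low-ALT baseline stratum in the synopsis reveals the ULN or shows how many such subjects were expected. The 40/60 U/L thresholds apply at screening, while SAP Section 6.2 takes baseline at Day 1, so a Day 1 value can be lower. SAP Section 6.1 repeats the ALT power paragraph without that stratum, and Protocol Section 10.3.1 and SAP Section 4.2 stratify by diabetes only.
- That the Week 24 MRI comparison is biased. No event count supports this.

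**Conclusion.** The point holds as a conflict of wording in a safety rule. Sections 6.3 and 12.4 cannot both be followed on whether study withdrawal after a first ALT above 5x baseline awaits confirmation, and they differ on which enzymes count. The >10x ULN rule is mandatory in two places and discretionary in two others. Ending study participation does not fit Sections 6.1 and 10.1, with partial relief from Sections 6.3.1, 10.4.4 and 10.4.6. Section 6.1 applies directly only if the rise counts as an adverse reaction; Section 10.1 covers anyone off drug.

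The size cannot be stated. The documents give no expected number of such rises among the 60 subjects, and it may be zero; the ULN is not given, and no limit on baseline ALT should be drawn. The textual mismatch itself rests on no assumption. It should be corrected because it concerns liver safety and the correction is cheap, not because harm or bias has been shown.

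**What to change.** Put one rule in both Section 6.3 and Section 12.4: hold study drug at the first ALT or AST above 5x baseline, repeat within 48 hours, and permanently discontinue study drug if the repeat is still above 5x baseline. The sponsor's clinicians could choose to stop permanently at the first value instead; what matters is that both sections say the same.

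Then:

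- Give the >10x ULN rule the same wording in the Section 12.4 footnote, Grade 4 row and list, and in Section 10.4.7, and say whether it needs confirmation.
- State that the >5x baseline rule overrides the Grade 3 interrupt-and-resume rule when both are met.
- Replace withdrawal from the study with discontinuation of study drug in Sections 6.3 and 12.4, including the footnote and Grade 4 row, with scheduled visits and the Week 24 MRI continuing.

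The cost is a protocol amendment and a site letter. Subjects whose repeat is not confirmed lose up to about 48 hours of dosing (2 doses a day x 2 days = 4 doses) plus the time to get the result. Subjects who stop drug carry the burden of the remaining visits, which they may decline.

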10.4.7 Criteria for Discontinuation of Study Treatment

Study medication may be discontinued in the following instances

- Intercurrent illness that would, in the judgment of the investigator, affect assessment of clinical status to a significant degree
- Any concern for drug-induced liver injury as defined by change from baseline liver aminotransferases according to the following criteria:
 - ALT or AST > 10 x ULN
 - ALT or AST > 5 x ULN for more than 2 weeks
 - ALT or AST > 3 x ULN and total bilirubin > 2 x ULN or INR > 1.5
 - ALT or AST > 3 x ULN with the appearance of fatigue, nausea, vomiting, right upper quadrant abdominal pain, fever, rash or eosinophilia (> 5%).
- Unacceptable toxicity, as defined in the toxicity management section of the protocol, or toxicity that, in the judgment of the investigator, compromises the ability to continue study-specific procedures or is considered to not be in the subject's best interest.
- Subject request to discontinue for any reason
- Subject noncompliance
- Pregnancy during the study
- Sponsor discretion

- Discontinuation of the study at the request of TaiwanJ. Pharmaceuticals, any Regulatory Authorities or an IRB/IEC.

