11.2.2 Laboratory Safety Assessments

All laboratory tests following randomization will be performed by a study approved laboratory service. Samples will be drawn at sites and forwarded under appropriate conditions to the approved laboratory. The laboratory will communicate all test results to site study personnel. The Laboratory Assessing Physician will immediately notify sites of any values which lie outside pre-specified ranges. Screening samples, prior to initiation of study drug, may be analyzed at site.

Sites will be immediately notified of any test results that lie outside of pre-specified ranges. Site personnel will not be expected to transcribe results from the laboratory into the CRF, although abnormal results that are considered clinically significant should be entered in the CRF as adverse events. Screening assessments, prior to initiation of study drug, may be performed at sites. Sites are discouraged from performing additional routine investigations locally, but site personnel are permitted to perform any investigations at any time that may be necessary to safeguard patient welfare.

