11.4 Communication of Laboratory Results to Sites

All laboratory results will be communicated directly to sites by fax or other means. All laboratory results which equate to an NCI CTCAE grade 3 or above toxicity will be escalated for internal medical review by the contract research organization and/or medical monitor.

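### Section 12.4 puts ALT/AST >3–5×ULN with bilirubin >2–2.5×ULN in a no-change row and also on the consider-stopping list, with no rule of precedence and no repeat time tied to the pattern

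*Protocol*

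**What the plan says.** Protocol section 12.4 grades liver tests on the DAIDS scale. The Grade 2 row covers ALT 2.6–5.0×ULN, AST 2.6–5.0×ULN, total bilirubin 1.6–2.5×ULN and INR 1.4–1.5, joined by and/or, so one abnormal value or several together fall in it. The only action shown is "Non treatment modification".

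The list directly under the table begins "Discontinuation of treatment should be considered if". Its third item is the combination that section 10.4.7 also carries: "ALT or AST > 3 x ULN and total bilirubin > 2 x ULN or INR > 1.5". Section 10.4.7 introduces its criteria with "Any concern for drug-induced liver injury as defined by change from baseline liver aminotransferases", under an opening that permits stopping study medication but does not require it.

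Fixed repeat times come from two other triggers. Section 12.4 sets a one-week repeat for ALT 5–10×ULN, and retesting with examination within one week when liver enzymes exceed 3 times the subject's baseline. Section 6.3 adds weekly monitoring when ALT exceeds 3 times baseline. Neither of the baseline rules depends on grade.

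**The concern.** Raised aminotransferases together with raised bilirubin is a pattern that the protocol itself names as a drug-induced liver injury concern. Within part of its range, the table tells the site to change nothing. A site that works from the table row could keep the subject on drug with no early repeat. A site that works from the list would consider stopping. Two sites could handle the same results differently and each could cite section 12.4.

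The bilirubin part is not background. Exclusion 19(g) in section 8.2 keeps out anyone with bilirubin above normal, except for Gilbert's syndrome or an extrahepatic source. For all other subjects, bilirubin above 2×ULN has arisen since screening.

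**Working it through.** There is no stated figure to reproduce. The check intersects the two rules and then asks who has a fixed repeat.

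**1. Overlap of the Grade 2 row with the third criterion (section 12.4)**

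- ALT or AST: 2.6–5.0×ULN against >3×ULN gives >3 to 5.0×ULN.
- Total bilirubin: 1.6–2.5×ULN against >2×ULN gives >2 to 2.5×ULN.
- INR: 1.4–1.5 against >1.5 gives no overlap.

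The conflict is therefore confined to the enzyme-plus-bilirubin limb. No sentence in 12.4, 10.4.7 or 6.3 ranks the list against the row.

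**2. Who in the band is caught by the 3-times-baseline rule**

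For an enzyme with baseline *b* (in ×ULN), the rule starts above 3*b*. Within the >3–5×ULN band:

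- *b* = 1.0: 3 × 1.0 = 3.0×ULN, so the whole band is covered.
- *b* = 1.33: 3 × 1.33 = 4.0×ULN, so half is covered.
- *b* = 1.67: 3 × 1.67 = 5.0×ULN, so none is covered; the same holds for any higher baseline.

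The ULN for toxicity grading is not given in U/L, so it has to be assumed. Take Day 1 ALT at the entry minimum (40 U/L for women, 60 U/L for men; section 8.1). Three times baseline is then 120 and 180 U/L.

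| Assumed ALT ULN (U/L) | Rule starts above, women | Rule starts above, men |
|---|---|---|
| 20 women / 30 men (normal range in the protocol synopsis) | 120/20 = 6.0×ULN | 180/30 = 6.0×ULN |
| 40 (alternative limit in SAP 5.2) | 120/40 = 3.0×ULN | 180/40 = 4.5×ULN |
| 50 (assumption) | 120/50 = 2.4×ULN | 180/50 = 3.6×ULN |

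At 20/30 the ALT rule never operates inside the band for a subject whose baseline is at or above the entry minimum. At ULN 40 it covers the whole band for a woman at the minimum. It covers none of it once baseline reaches about 67 U/L (5 × 40 = 200; 200/3 = 66.7). AST has no lower entry limit, so a rise from near-normal AST can bring the section 12.4 rule into play at any ULN.

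**3. Wait for a subject in the band who is not above 3 times baseline**

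From week 4 on, scheduled visits are 28 days apart, each with a ±4-day window (section 10.2.1). Using weeks 4 and 8:

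- Shortest: (56 − 4) − (28 + 4) = 20 days.
- Longest: (56 + 4) − (28 − 4) = 36 days.

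**The case against.** The best defence is that the list is a natural overlay. The table grades single laboratory values, the list beneath adds combinations, duration and symptoms with no grade limit, and a specific criterion normally qualifies a general row. Section 10.4.7 repeats the criterion as a reason to stop, so an investigator meets it twice. This is a sensible reading and many sites would adopt it. But the row's and/or wording expressly takes in the combination, and no text tells the site to prefer the list.

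General cover also exists. Section 6.3 gives as a ground for withdrawal "Subject has laboratory safety assessments that reveal clinically significant worsening from baseline values". Section 11.2.2 says "Sites are discouraged from performing additional routine investigations locally, but site personnel are permitted to perform any investigations at any time" where patient welfare needs it, and has clinically significant abnormal results recorded as adverse events. Section 12.4 has adverse events followed until they resolve or are considered chronic or stable. A medical monitor and a data review board look at safety. All of this permits action. None of it sets a repeat time or calls for a decision on this pattern.

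Several stronger readings are tempting but go too far:

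- *That the row overrides a mandatory stop.* It does not; both discontinuation texts are discretionary.
- *That nothing fixes a repeat for anyone in the band.* The 3-times-baseline rules do so for some subjects, whatever the grade.
- *That central escalation would miss these subjects.* Section 11.4 says "All laboratory results which equate to an NCI CTCAE grade 3 or above toxicity will be escalated for internal medical review", but that is the CTCAE scale while the table is DAIDS. The documents give no CTCAE cut points, so the inference cannot be drawn.
- *That the symptom criterion conflicts in the same way.* The table grades laboratory values only, so a symptom-based criterion is an addition to it and not a rival instruction.

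One caveat concerns the extracted table, where a single action appears to serve both the drug-related and the non-drug-related columns. If that cell is not merged, drug-related Grade 2 has no action at all, and the link to the list is still missing.

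**Conclusion.** The point holds as a gap in precedence. For ALT or AST >3–5×ULN with total bilirubin >2–2.5×ULN, section 12.4 says both to change nothing and to consider stopping, and no text settles which. No repeat time is tied to this combination. Subjects in the band whose enzymes are not above 3 times baseline have no fixed repeat before the next scheduled visit: 28 days from week 4 on, 20–36 days with windows.

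The band is narrow, few of the 60 subjects would be expected in it, and the documents do not support a count or a share. How many of them the 3-times-baseline rule would catch depends on an undefined ULN and on each subject's baseline ALT and AST. The overlap itself depends on neither. This is a cheap improvement for patient safety and does not affect the trial's efficacy inference.

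**What to change.** Add to the Grade 2 row, to the section 12.4 text and to section 10.4.7:

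*The listed discontinuation criteria apply regardless of grade. A subject with ALT or AST >3×ULN and total bilirubin >2×ULN is not managed under the Grade 2 no-modification action, but has repeat testing and evaluation within 1 week and is referred to the medical monitor for a decision on stopping.*

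State alongside it that the Grade 3 and Grade 4 actions are unchanged. This matters because above 10×ULN the table terminates treatment while the list only asks that stopping be considered, and the new sentence must not soften the table there.

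The change is wording in one table row and two sections, with no new routine visit or test. The one-week repeat and the referral are new requirements for this pattern, but they use the protocol's own repeat interval and a medical monitor already provided for in section 13.6. The downside is a few extra repeat tests and possibly a few interruptions. Some may fall on subjects admitted with Gilbert's syndrome, who can meet the bilirubin part without liver injury; the medical monitor's decision allows for that.
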